2 STUDY OBJECTIVES

[figure not shown]
The trial seeks to determine whether –

- a. Seasonal vaccination following priming with the RTS,S/AS01 malaria vaccine would be non-inferior to SMC SP + AQ in preventing malaria in children in the areas of the Sahel and sub-Saharan Africa where malaria is still a major public health challenge and whether it would be easier to deliver.
- b. RTS,S/AS01 would provide additional, useful and cost effective protection against malaria if given together with SMC in areas with highly seasonal malaria transmission and reduce the risk of the emergence of resistance to the antimalarials used for SMC.

3 STUDY AREA

The trial will be conducted in Houndé health district, Burkina Faso and in Bougouni Koulikoro district, Mali. The Houndé district is situated 300 km from Ouagadougou and 100 Km from Bobo-Dioulasso where the CHUSS, the 2nd National Reference Hospital (University Hospital), is located and which is also a base of the IRSS. The study site in Mali is the district of Bougouni in the region of Sikasso, Mali, 150 km south of Bamako where the MRTC is based.

Figure 1 : Map of Mali and Burkina Faso showing the two sites.

The population of Houndé district belongs primarily to the Bwaba ethnic group and that of Bougouni primarily to the Bambara and Fula ethnic groups. Farming is the main occupation in each area. Each district has a district hospital.

Malaria, due predominantly to *Plasmodium falciparum*, is highly seasonal in both districts with over 80% of cases occurring during the rainy season (July – October) and during the following month. The prevalence of *P. falciparum* malaria in school age children in December 2015 was 53% in Bougouni and 62% in Houndé. The main malaria vector in each study area is *Anopheles gambiae* ss. A high proportion of children sleep under an ITN in Bougouni (96%) but the percentage is less in Houndé. The first line treatment for malaria in the public health system is artemether /lumefantrine in each district. Cases of uncomplicated malaria are treated at one of the health centres in the district and in Bougouni some cases are treated in the community by trained community health workers. Cases of severe malaria are managed in the district hospital. During the SMC + AZ trial the incidence of clinically suspected meningitis in children aged 3 - 59 months in Bougouni was approximately 0.11 per 1,000 per year and that of cerebral malaria 0.88 per 1,000 per year.

During 2014-2017, Houndé and Bougouni districts were the sites of a trial, involving approximately 20,000 children aged 3-59 months, which evaluated the impact of adding azithromycin to the SP +

AQ used for SMC in preventing overall mortality and hospital admissions with non-traumatic illnesses. The trial found that addition of azithromycin to the antimalarials used for SMC did not reduce the incidence of death or admission to hospital with a condition not due to trauma, its primary end-point, although it led to a modest reduction in the incidence of clinical attendances with respiratory, gastrointestinal or skin infections [14]. This trial finished at the end of 2016 allowing a smooth transition to the new trial, incorporating many of the well trained staff who had conducted the previous study. Field laboratories, which are equipped to undertake parasitological and haematological investigations, have been established at each district hospital and efficient data management systems set up.

In Mali, vaccines are stored at MRTC, Bamako, Mali. The MRTC has a long history (> 12 years) of testing vaccines including collaboration with GSK, the WRAIR, the NIAID/NIH and Sanaria. Vaccines are stored in a cold room with continuous monitoring of the temperature devices with alarm and telephone SMS and an email alert system. The system is also equipped with two back-up generators. Only authorized personnel have access to the cold room. The cold room has a capacity of 14.28 m³ (2.45m long x 2.45m wide x 2.38m high). Standard operating procedures are in place for vaccine reception, storage in the cold room and transfer to field sites on a daily basis. In Burkina Faso, vaccines are stored at IRSS, in Bobo-Dioulasso where there is a dedicated storage room for drugs that has pharmaceutical refrigerators with dynamic cooling and an automatic defrosting system, power failure and open door alarms. The room is air conditioned 24 hours a day and the temperature maintained at 22°C average with temperature and humidity controllers.

4 COMMUNITY SENSITISATION

The objectives of the study and the way in which it would be conducted were discussed with staff of the national malaria control programmes (NMCPs) and expanded infant immunisation programmes (EPIs) in both Burkina Faso and Mali and their support for the trial obtained in principle. These discussions have been continued. Community approval was sought through meetings with leaders of the study communities and through open meetings held in the study communities. Community leaders were consulted prior to the start of the intervention on the best ways of achieving high compliance with vaccination, drug delivery and follow-up.

5 TRIAL POPULATION

After obtaining permission from the community leaders for the trial, a household census was conducted in February – March 2017 and all households within the study areas with children 5-17 months of age on April 1st 2017 were enumerated. At the census, a preliminary screening of potentially eligible children was undertaken. Potentially eligible children and their caretakers were visited again and written informed consent was obtained from their caretakers for their inclusion in the trial before the administration of the first dose of study vaccines. Children entered into the trial were assigned a unique ID number and their demographic data (date of birth and/or age, and gender), use of insecticide treated nets (ITN) and history of receiving SMC during the last transmission season were collected. The census data was updated in April/May 2018 and 2019 prior to the administration of the booster doses of vaccine. Eligible children were allocated randomly to one of the three study arms in permuted blocks of 12 using standard randomisation procedures (table). Children who had a history of receiving SMC in the previous years were distributed equally between the three study groups

A child was eligible for inclusion in the trial if -

- a. The child was a permanent resident of the study area and likely to remain a resident for the duration of the trial.
- b. The child was 5 - 17 months of age at the time of first vaccination.
- c. A parent or legally recognised guardian provided informed consent for the child to join the trial.

A child was ineligible for inclusion in the trial if -

- a. The child was a transient resident in the study area.
- b. The child was in care.
- c. The age of the child was outside the stipulated range.
- d. The child had a history of an adverse reaction to SP or AQ.
- e. The child had a serious underlying illness, including known HIV infection, unless this was well controlled by treatment, or severe malnutrition (weight for age or mid arm circumference Z scores < 3 SD).
- f. The child was known to have an immune deficiency disease or was receiving an immunosuppressive drug.

- g. The child had previously received a malaria vaccine.
- h. The child was enrolled in another malaria intervention trial.
- i. The parents or guardians did not provide informed consent.

Table. Study groups

	Group1 (SMC alone)	Group2 (RTS,S alone)	Group3 (RTS,S+SMC)
Year1: April-June	Rabies vaccine x 3	RTSS/AS01 x 3	RTSS/AS01 x 3
Aug-Nov	SMC x 4	SMC placebo x 4	SMC x 4
Year2: Aug-Nov	HepA vaccine x 1	RTSS/AS01 x 1	RTSS/AS01 x 1
	SMC x 4	SMC placebo x 4	SMC x 4
Year3: Aug-Nov	HepA vaccine x 1	RTSS/AS01 x 1	RTSS/AS01 x 1
	SMC x 4	SMC placebo x 4	SMC x 4

SMC or placebo is given at monthly intervals on four occasions during the malaria transmission season.

6 SAMPLE SIZE

Approximately 3,000 children have been recruited in Burkina Faso and a similar number in Mali (total 6,000) and these children will be followed for three years. A low dropout rate of around 5 % per year (15% overall) is anticipated based on findings from the previous SMC+AZ study, although it is possible that the dropout rate may be higher during a vaccine trial as a vaccine trial has not been conducted previously in the study districts. Since the relative efficacy of SMC and RTS,S/AS01 is uncertain, the conservative approach of recruiting equal numbers of children into each arm of the study (2,000 per arm) has been followed. Results obtained over a period of three years of observation in the two study sites will be combined for the primary analysis of the incidence of clinical malaria. An analysis will also be undertaken of efficacy in each year of the trial to estimate the efficacy of administration of a booster dose. It is not anticipated that a formal unblinded interim analysis will be undertaken although a preliminary analysis by an independent statistician will be undertaken early in 2020 to provide guidance as to whether the trial should be extended.

During the SMC study in the trial sites, the incidence of clinical episodes of malaria during the first year of the study (2014) was 442 and 382 per 1000 children in Mali and in Burkina Faso respectively. Complete morbidity data was not available for the second year of the study (2016). For the sample size calculations, a conservative incidence rate of 300 cases per 1000 children over a calendar year was assumed. Using a two sided 95% confidence interval, a three-arm study which enrolled 2000 children in each arm (1000 per arm per centre) would have, for the non-inferiority comparisons, 90% power to exclude a relative difference in incidence between RTS,S/AS01 and SMC given alone of 16.1% over the three-year study period and of 28.6% or more for each individual year. The study would also have 80% power to exclude a relative difference in incidence of 13.9% over the whole study period and of 24.7% in each year. The differences that could be detected will be smaller if, as suspected, the incidence of clinical malaria is greater than 300 cases per 1,000 children per year. For the superiority comparisons of the combined interventions with SMC alone, using a two-sided 95% confidence interval, the study would have 90% power to detect a difference greater than 11.1% over the three years of the study and of 19.2% in each year.

For the analysis of the serological response to RTS,S/AS01, comparisons will be made between mean anti-CSP antibody titres pre and post the primary series of vaccination and before and after the two subsequent booster doses. Based on the standard deviations in antibody titres observed in children enrolled in the RTS,S/AS01 phase 2 and phase 3 trials, inclusion of around 160 individuals in each group (pre and post vaccination at each of the three time points) will give a study with approximately 80% power to detect a difference of 25% - 30% in mean titre between children who receive RTS,S/AS01 with or without co-administration of SMC.

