the intention to treat analysis. Children who received all scheduled doses of SMC, or treatment for a clinical episode of malaria at a time when SMC would have been given, or all scheduled doses of vaccine will be included in the per protocol analysis for each year of the study. Results obtained in Burkina Faso and Mali will be analysed separately but the study is only powered to meet its primary and major secondary end-points if results from both countries are combined. Additional sub-analyses will include analysis by age, gender, bed net use during the transmission season, as determined by the history obtained at the cross-sectional surveys, and socio-economic status as determined by the educational level and occupation of the child's family.

A formal interim analysis will not be undertaken. However, a preliminary analysis of the key trial clinical trial end-points will be undertaken by an independent statistician early in 2020 in order to decide whether the trial should be continued until children reach the age of five years, the age at which SMC is no longer given.

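### Protocol section 6: the printed non-inferiority and superiority differences cannot both come from the one stated set of inputs; non-inferiority needs roughly half the effective sample size of superiority

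*Combined protocol and SAP*

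**What the plan says.** Section 6 of the final protocol (the December 2016 protocol prints the same power figures) lists its inputs once. The design is one that "enrolled 2000 children in each arm (1000 per arm per centre"), and "a conservative incidence rate of 300 cases per 1000 children over a calendar year was assumed". A two-sided 95% confidence interval is named for each comparison.

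The resulting claims are:

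- Non-inferiority, RTS,S/AS01 against SMC: "90% power to exclude a relative difference in incidence between RTS,S/AS01 and SMC given alone of 16.1% over the three-year study period"; the single-year figure is 28.6%.
- The same comparison at lower power: "80% power to exclude a relative difference in incidence of 13.9% over the whole study period and of 24.7% in each year".
- Superiority, combined arm against SMC: the trial "would have 90% power to detect a difference greater than 11.1% over the three years of the study and of 19.2% in each year".

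On dropout, "A low dropout rate of around 5 % per year (15% overall) is anticipated", but the section does not say whether or how this enters the calculation. Nor does it state a formula, a scale or an allowance for repeat episodes. It does say that results "in the two study sites will be combined for the primary analysis of the incidence of clinical malaria", and section 15 adds that "the study is only powered to meet its primary and major secondary end-points if results from both countries are combined".

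**The concern.** The two comparisons share the endpoint, arm size, incidence, follow-up and interval. With equal arms and a true ratio of 1 for non-inferiority, the two detectable differences should then be close, differing only through the asymmetry between an increase and a decrease. Instead the ratios are 16.1/11.1 = 1.45 over three years and 28.6/19.2 = 1.49 for one year, close to the square root of 2. That pattern suggests a factor of about 2 in information between the two sets.

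These are the protocol's power figures for two objectives that the SAP ranks equally, and the SAP's non-inferiority paragraph still points back to the protocol for the power at margins below 20%. A reader cannot tell which set reflects the planned trial.

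**Working it through.** **Inputs.** Rate 0.30 per child-year; two-sided 95% interval (z = 1.960); z = 1.282 for 90% power and 0.842 for 80%. The dropout handling is my assumption: 0.95^k of children retained in year k. Three-year exposure is then 0.95 + 0.9025 + 0.8574 = 2.7099 years per child, or 0.8130 expected events. For one year I use year-3 retention, 0.8574, or 0.2572 events. Events are treated as Poisson.

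**Step 1: reproduce the printed figures and read off the arm size.** On the relative-difference scale, with Z the sum of the two z-values, d the printed difference and m the expected events per child:

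- Non-inferiority: N = 2(Z/d)² / m
- Superiority: N = (2 − d)(Z/d)² / m

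Example: 2 × (3.2415/0.161)² = 810.7 events per arm; 810.7/0.8130 = 997 children. On the log scale, d in (Z/d)² is replaced by ln(1 + d) for non-inferiority; for superiority it is replaced by ln(1 − d) and the factor 2 − d by 1 + 1/(1 − d).

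| Printed figure | Power | N per arm, relative | N per arm, log |
|---|---|---|---|
| NI 16.1%, three years | 90% | 997 | 1,160 |
| NI 13.9%, three years | 80% | 999 | 1,140 |
| NI 28.6%, one year | 90% | 999 | 1,291 |
| NI 24.7%, one year | 80% | 1,000 | 1,253 |
| Superiority 11.1%, three years | 90% | 1,982 | 1,984 |
| Superiority 19.2%, one year | 90% | 2,004 | 2,011 |

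Run forward on the relative scale, N = 1,000 gives non-inferiority 16.08 / 28.58 / 13.90 / 24.70% and N = 2,000 gives superiority 11.05 / 19.22%. All six printed values are recovered, but only by changing the arm size between the comparisons.

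**Step 2: does the result depend on the assumed dropout?** No. Arm size, rate, retention and any common variance factor enter only through the effective number of events per arm, so a shared value cancels.

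- Relative scale: 16.1% fixes 810.7 effective events. Solving d = 3.2415 × √((2 − d)/810.7) gives superiority 15.5%, against 11.1% printed. For one year, 28.6% fixes 256.9 events and gives 26.6%, against 19.2%.
- Log scale: 943.0 and 332.1 effective events give 14.4% and 23.7%.

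**Step 3: what 2,000 per arm gives on one basis.** Expected events per arm are 2,000 × 0.8130 = 1,626.

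- No overdispersion. Three-year non-inferiority is 3.2415 × √(2/1,626) = 11.4% at 90% power and 9.8% at 80% (12.0% and 10.3% on the log scale). Superiority is 11.1%, and 19.2% for one year.
- Variance factor 2 for both. Effective events are 813. Non-inferiority stays as printed on the relative scale. Superiority becomes 15.4% (three years) and 26.6% (one year), and its power at 11.1% is Φ(0.111/√(1.889/813) − 1.96) = 63%.

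**Step 4: the 15% claim in section 15.** Power at 15% over three years is 99.0% (relative) or 97.9% (log) with no overdispersion, and 85.6% or 80.5% with a factor of 2. The claim of more than 80% holds either way.

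**Step 5: do the SAP's own power statements settle the cause?** Take 2,000 per arm, 200 per 1,000 per year as the reference-arm rate, and the same retention: 2,000 × 0.2 × 2.7099 = 1,084 events per arm.

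- 80% power to exclude a 20% excess needs 2 × (2.8016/ln 1.2)² = 472 events. Plain Poisson would give about 99% power; the implied factor is 1,084/472 = 2.3.
- 90% power for the lower limit to exclude 15% at a true 30% efficacy needs (1 + 1/0.7) × (3.2415/ln(0.85/0.70))² = 677 events. Plain Poisson would give about 98%; the implied factor is 1,084/677 = 1.6.

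Both statements sit below Poisson power, but by different amounts, and the SAP declares no factor.

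**The case against.** Three objections carry weight.

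First, the clean match to 1,000 and 2,000 is partly a choice of convention. It needs the relative scale and, for the one-year figures, year-3 retention, which is odd for a figure said to apply to each year. With year-1 retention the one-year sizes are about 901-903 and 1,808; with no loss, 856-858 and 1,718. This stands, so the round numbers should not be leaned on. The mismatch itself survives each of these choices.

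Second, a reader might infer that the per-centre arm size was used by mistake, so that non-inferiority power is understated (about 99% at 16.1%) and the superiority figures are sound. The documents do not support going that far. The per-centre number does appear in the sentence, but the planned analysis uses a robust standard error for repeat episodes, and the SAP's later statements also fall short of Poisson power, by factors of 1.6 to 2.3. An undeclared allowance for repeat episodes is at least as plausible. The opposite inference, that superiority power was overstated because the allowance was left out there, is equally unproven: no factor is printed anywhere.

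Third, the SAP has since set its own incidence, margin (20%) and power statements, and recruitment was complete. This also stands, and it limits the consequence to the record of how the trial was sized.

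**Conclusion.** The printed non-inferiority and superiority differences are jointly impossible on the stated inputs. Non-inferiority needs between half and two-thirds of the effective sample size of superiority: half on the relative scale (about 1,000 against 2,000 per arm), 57% to 65% on the log scale (about 1,140-1,290 against 1,980-2,010). Standard event-rate approximations and a two-sided 95% interval for both comparisons are assumed; the dropout assumption affects the implied sizes but not the contradiction.

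Which set is wrong cannot be determined from the documents, and neither explanation should be preferred. Nothing that decides the trial turns on it: section 15's 15% claim holds under both, and the margin, enrolment and decision rules are untouched. Severity is minor.

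**What to change.** In section 6, or in a note to the SAP's sample size section, state for both comparisons the arm size, how dropout enters, the scale, and one variance factor consistent with the planned robust-error analysis. Then restate whichever set does not follow. The values in step 3 show what to expect: if no overdispersion is declared, three-year non-inferiority moves to about 11.4-12.0% (90% power) and 9.8-10.3% (80%) and superiority stays; if a factor of 2 is declared, superiority moves to about 15.4% and 26.6% and non-inferiority stays on the relative scale. If the original calculation file exists, it should settle which applies. The cost is a text correction.

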15 ANALYSIS

The primary endpoint of incidence of all episodes of clinical malaria over the study period will be analysed using Cox regression models with a robust standard error to account for clustering of episodes within individuals (i.e. the Andersen-Gill extension of the Cox model). This will estimate the total effect of the interventions. The proportion of children in each group who experience one episode of malaria will be compared as a secondary outcome using Kaplan-Meier estimates: evidence for provision of complete protection through the combination of SMC and vaccination each year will be explored using recently published methods [19, 20]. For the comparison of RTS,S/AS01 plus SMC to the other interventions, a standard superiority comparison will be performed, calculating two-sided 95% confidence intervals for the hazard ratio. For the non-inferiority comparison of RTS,S/AS01 to SMC, the two-sided 95% confidence interval for the hazard ratio will be compared to a pre-specified non-inferiority margin. The trial is powered to have more than 80% power to exclude a difference of 15% in the incidence of clinical malaria over the study period, a difference considered to be clinically important. Demonstration of a smaller difference would require a substantially larger trial and is considered to be not clinically relevant. If the lower limit of the 95% does not overlap zero (i.e. it is clear that RTS,S is superior to SMC) then a superiority comparison will be performed as for the combined intervention.

A formal analysis plan will be prepared and approved by the Data Safety Monitoring Board (DSMB) appointed for the trial before the study code is broken. Both intention to treat and per protocol analyses will be undertaken. Children who received any dose of SMC or vaccine will be included in

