Children with a history of an adverse reaction to SP or AQ, known to have a serious underlying illness including known HIV infection not well controlled by treatment, having severe malnutrition (z scores < 3 SD) or known to have previously received a malaria vaccine were excluded from the trial.

Children known to have received SMC during the year prior to enrolment (either through the previous study in these districts (AZ-SMC, [NCT02211729](#)), or from the national programme) were not excluded from this study.

The list of eligible children in each country was sorted by location (village), age in months, gender and prior receipt of SMC, before assigning randomisation codes in permuted blocks of 9, to give an implicit stratification on these factors.

Sample size and Study Design

Based on the calculations described below, the trial aimed to recruit approximately 3,000 children in Burkina Faso and 3,000 in Mali (total 6,000) who would be followed for three years. A low dropout rate of around 5% per year (15% overall) was anticipated based on findings from the previous trial conducted in the same study areas.

In Burkina Faso and Mali, 2777 and 3143 children, respectively, received the first dose of study vaccine.

Superiority comparison: The trial was designed to compare the two interventions combined with either used alone. The study is powered to i) assess the statistical evidence against the null hypothesis of no difference between the combined group and either the SMC alone or RTS,S alone group, and ii) estimate the efficacy of the combined group relative to the single intervention groups with a relatively high degree of precision. This latter aspect is important because if the combined intervention is to be used in practice, it is necessary to show that adding RTS,S/AS01 to SMC has a clinically significant benefit.

After two years of follow-up, incidence of clinical malaria, as defined below, was approximately 200 cases per 1000 child-years at risk. With approximately 2000 individuals in each arm, if the

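### The final protocol's superiority detectable differences (11.1% and 19.2%) assume independent episodes at 300 per 1000; at the SAP's 200 per 1000, three-year power is about 76% before any clustering

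*Combined protocol and SAP*

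**What the plan says.** Section 6 of the final protocol sets out the superiority calculation:

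- Comparison and level: "For the superiority comparisons of the combined interventions with SMC alone, using a two-sided 95% confidence interval".
- Result: "the study would have 90% power to detect a difference greater than 11.1% over the three years of the study and of 19.2% in each" (19.2% being the single-year figure).
- Incidence: "a conservative incidence rate of 300 cases per 1000 children over a calendar year was assumed".
- Size: a three-arm study that "enrolled 2000 children in each arm (1000 per arm per centre").
- Attrition: "A low dropout rate of around 5 % per year (15% overall) is anticipated".
- Direction of any error in the rate: "The differences that could be detected will be smaller if, as suspected, the incidence of clinical malaria is greater than 300 cases per 1,000 children" (an annual rate).

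The same paragraph gives four non-inferiority figures for RTS,S alone against SMC alone: 16.1% (three years) and 28.6% (one year) at 90% power, and 13.9% and 24.7% at 80% power.

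Section 15 of the final protocol, and the SAP under Statistical methods, analyse all episodes per child with "Cox regression models with a robust standard error to account for clustering of episodes within individuals".

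The SAP, under Sample size and Study Design, reports: "After two years of follow-up, incidence of clinical malaria, as defined below, was approximately 200 cases per 1000 child-years at risk". On that basis it claims power close to 100% against no difference for a 30% reduction, and 90% power for the confidence interval to exclude 15% when efficacy is 30%. It does not return to 11.1% or 19.2%.

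**The concern.** Superiority of the combination is one of two objectives that the SAP ranks equally, and differences between study years are a pre-specified analysis. The 11.1% and 19.2% figures are the only minimum detectable superiority differences stated for either purpose. They depend on a variance that the planned analysis does not use and on an incidence that the SAP contradicts. Both discrepancies make the stated power too high. The two documents are contemporary: the last protocol amendment was approved on 7 April 2020 and the original SAP is dated 9 April 2020. If the figures stand, a reader of a non-significant overall or single-year result could take a benefit of 11% or 19% to have been reliably detectable when it was not.

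**Working it through.** **Inputs.** From protocol section 6: 2,000 per arm, two-sided 5%, r0 = 0.300 per child-year, 5% yearly dropout. From the SAP: r0 of about 0.200. D is a variance inflation factor, with D = 1 meaning independent episodes. Dropout is compounded and counted at each year's end.

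**Formula.** For a relative reduction d and PY person-years per arm:

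SE = √[D × r0 × (2 − d) / PY]; power = Φ(r0 × d / SE − 1.96).

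PY over three years = 2,000 × (0.95 + 0.9025 + 0.8574) = 5,420. PY in year 3 = 2,000 × 0.8574 = 1,715.

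**1. Reproducing the plan's superiority figures (r0 = 0.300, D = 1).**

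- Three years, d = 0.111: SE = √(0.300 × 1.889 / 5,420) = 0.01023; 0.0333 / 0.01023 = 3.257; power = Φ(1.297) = 90.3%. The 90%-power difference is 11.05%.
- Year 3, d = 0.192: SE = √(0.300 × 1.808 / 1,715) = 0.01779; 0.0576 / 0.01779 = 3.239; power = Φ(1.279) = 89.9%. The 90%-power difference is 19.2%.
- Without dropout (6,000 and 2,000 child-years) the differences would be 10.5% and 17.9%, so the printed figures already include dropout.

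**2. The non-inferiority figures in the same paragraph.** With equal true rates, the excludable difference is (1.96 + z_power) × √[2D / (r0 × PY)].

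| Figure | Printed | D = 1 | D = 2 |
|---|---|---|---|
| 90%, three years | 16.1% | 11.4% | 16.08% |
| 90%, one year | 28.6% | 20.2% | 28.58% |
| 80%, three years | 13.9% | 9.8% | 13.90% |
| 80%, one year | 24.7% | 17.5% | 24.70% |

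All four need D = 2, or equivalently 1,000 per arm with D = 1. The text does not say which was used.

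**3. Superiority power at the SAP's 200 per 1000, D = 1.**

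- Three years, d = 0.111: SE = √(0.200 × 1.889 / 5,420) = 0.00835; 0.0222 / 0.00835 = 2.659; power = Φ(0.699) = 75.8%. The 90%-power difference is 13.4% (13.5% on the log scale or with dropout taken as 5, 10 and 15%).
- With no dropout: 79.9%.
- If 200 is the average of three arms and only the combined arm is 11.1% lower, the SMC rate is 0.200 × 3 / 2.889 = 0.208. Power is then 77.3%, or 81.4% with no dropout as well.
- With the 5,920 children actually dosed (1,973 per arm): 75.2%.
- At an intermediate 250 per 1000: 84%.

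For a single year with d = 0.192, taking 200 per 1000 in that year:

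| Year | PY per arm | Power | 90%-power difference |
|---|---|---|---|
| 1 | 1,900 | 79.5% | 22.2% |
| 2 | 1,805 | 77.4% | 22.7% |
| 3 | 1,715 | 75.3% | 23.3% |

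**4. Clustering, three years.** No dispersion is given, so D is an assumed range.

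| D | Power for 11.1% at 300 | Power for 11.1% at 200 | 90%-power difference at 200 |
|---|---|---|---|
| 1.2 | 84% | 68% | 14.7% |
| 1.6 | 73% | 56% | 16.9% |
| 2 | 63% | 47% | 18.7% |

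**5. The SAP's own superiority statement (200 per 1000, 30% reduction).** Power against no difference exceeds 99.9% even at D = 2. For excluding 15%, the D that gives 90% power is [ln(0.70/0.85) / 3.2415]² / [1/(0.20 × 5,420) + 1/(0.14 × 5,420)] = 0.003588 / 0.002240 = 1.60. With D = 1 that power would be 98.4%.

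**The case against.** The printed figures are correct for their stated assumption, and 300 per 1000 was cautious against the 442 and 382 per 1000 seen in the same districts. Judging a design-stage rate by later data can be unfair, and the sentence about smaller differences is conditional. The SAP discloses the lower rate and restates superiority power for an effect it regards as clinically significant. Results will be reported with confidence intervals, and what a result rules out is read from the interval, not from planned power. Observation ended on 31 March 2020, so no operational decision depends on section 6. The 200 is approximate, not given by arm, and covers two years. The endpoint wording also differs: the protocol counts treatment by community health workers, whereas the SAP refers to study health centres and hospitals.

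Much of this stands, and it limits the finding. A reader might infer that the superiority objective is underpowered. The documents do not support that, because power at the SAP's 30% effect is near 100% even with doubled variance. A reader might also take 76% as a ceiling, but other readings of the rate and dropout give 77% to 81%. Nor can the doubled variance behind the non-inferiority figures be called a clustering allowance, since 1,000 per arm gives the same numbers.

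The objection does not remove the discrepancy. The SAP's restatement covers only a 30% effect, so the 11.1% and 19.2% figures remain uncorrected. The final protocol still expects incidence above 300, although a lower figure appears in an SAP dated two days after that protocol's approval.

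**Conclusion.** The point holds in limited form. The superiority detectable differences in section 6 are out of date against the SAP's incidence, omit clustering, and use half the variance of the non-inferiority figures beside them. At 200 per 1000 with independent episodes, power is about 76% for 11.1% over three years (up to about 81%) and 75% to 80% for 19.2% in a single year, against a stated 90%. The differences with 90% power are about 13.5% and 22% to 23%.

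These results assume that the SAP's approximate two-year rate applies to the SMC arm, or to the three-arm average where stated, and to every year. Any clustering loss is additional, but its size cannot be fixed from the documents: 68%, 56% and 47% are illustrations at inflation of 1.2, 1.6 and 2. The finding concerns stated sensitivity to small effects. It does not call into question the planned test or the SAP's power at a 30% effect.

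**What to change.** In protocol section 6:

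- Restate the superiority detectable differences at the SAP's incidence, naming the formula, the dropout and the variance inflation. Without inflation they are about 13.5% over three years and 22% to 23% in a single year. Over three years they are about 17% at inflation of 1.6 and 19% at 2.
- Estimate the inflation from blinded, pooled counts of episodes per child, or make it consistent with the non-inferiority figures. State whether those figures used a design effect of 2 or 1,000 per arm.
- Remove or correct the statement that differences will be smaller because incidence is suspected to exceed 300.
- Reconcile the section with the SAP's Sample size and Study Design text.

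The cost is wording, one blinded dispersion estimate from existing data if that route is chosen, and less favourable stated figures. Enrolment and the planned analysis do not change.
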